### **Study participants**

Potential participants will be recruited by the main researcher

Inclusion criteria:

1. Patients who are hospitalized with upper extremity weakness due to stroke on the same side which confirmed with computed tomography (CT) scan or structural magnetic resonance imaging (MRI), in the acute phase
2. Men and women aged more than 18 years old
3. Willing to participate

Exclusion criteria:

1. Cognitive impairment (MoCA-Ina score less than 26)
2. Impaired consciousness (GCS score less than 15)
3. Unstable medical conditions at time of hospitalization
4. Patients with pacemaker

5. Having other injury or dysfunction in the impaired side of upper extremity that caused restrictions on the range of joint movement and muscle weakness, such as fractures, periarthritis, or moderate-severe pain
6. Diagnosis of other neurological disease or disorders in addition to stroke (e.g., traumatic brain injury, neuropathy or radiculopathy)
7. Get treated in isolation room
8. Hypersensitivity to gel electrodes

Drop out criteria:

1. Unable to do 2 or more follow up session
2. Withdrawn by themselves

Confounding factor:

1. Stroke location
2. Stroke size
3. Spasticity
4. Rehabilitation program
5. Compliance rehabilitation
6. Stroke risk factor

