## **Data Analysis**

Before data analysis is carried out, the data is checked for completeness and accuracy, tabulated, coded, and entered into the computer. The next data analysis aims to describe the dependent and independent variables so that it can help further analysis in more depth. Apart from that, descriptive analysis is also used to determine the characteristics of the research subjects, who are the research samples.

Data analysis to see an overview of the proportions of each variable that will be presented descriptively can be broken down into descriptive analysis and hypothesis testing. Numerical scale data such as age and others are presented with a mean and standard deviation, a maximum value, and a minimum value. The sample characteristic data in the form of categorical data is presented in a frequency distribution table. Data is recorded in the research form that has been created, then editing, verification, coding, and data entry are carried out, and then data analysis

is carried out. Statistical analysis according to research objectives and research hypotheses Data are presented as percentages (%) for categorical variables and mean  $\pm$  standard deviation (SD) for continuous variables. Statistical analysis begins with this normality test aims to find out whether the data is normally distributed or not. The statistical test used to test the data is normally distributed or not, with Shapiro Wilks (because n is less than 50). Numerical variables between pairs of two groups is compared using the paired T test if the data is normally distributed and the alternative Wilcoxon test. Numerical variables between pairs of more than two groups is compared using the repeated ANOVA test if the data is normally distributed and the alternative Fredman test. The McNemar and Marginal Homogeneity tests are used for paired categorical data. The significance of statistical test results is determined based on a p value of  $<0.05$ .

The data obtained was recorded in a special form and then processed using the SPSS version 24.0 for Windows program.

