#### Data Dasar

Nama	:	Lama tinggal RS	:
No. MR	:	Diagnosa	:
Jenis Kelamin	: L/P	Stroke ulang	: Ya/Tidak
Tanggal lahir	:	Sisi Lesi Otak	:
Usia	:	Sisi Stroke	:
Pendidikan	:	Tangan dominan	:
Faktor Risiko	:		

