#### Pemeriksaan Fisik

Tekanan Darah	:	RR	:
---------------	---	----	---

Nadi	:	Suhu	:
------	---	------	---

SpO2	:	BMI	:
------	---	-----	---

VAS	:	NIHSS score	:
-----	---	-------------	---

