## Penilaian dan Pemeriksaan MMT, FMA-UE dan sEMG

No	MMT Score	FMA-UE Score	sEMG				
			Deltoid	Biceps	Triceps	Wrist flexors	Wrist extensors
Pemeriksaan 1			K: LK: A:	K: LK: A:	K: LK: A:	K: LK: A:	K: LK: A:
Pemeriksaan 2			K: LK: A:	K: LK: A:	K: LK: A:	K: LK: A:	K: LK: A:
Follow Up 1			K: LK: A:	K: LK: A:	K: LK: A:	K: LK: A:	K: LK: A:
Follow Up 2			K: LK: A:	K: LK: A:	K: LK: A:	K: LK: A:	K: LK: A:
Follow Up 3			K: LK: A:	K: LK: A:	K: LK: A:	K: LK: A:	K: LK: A:

\*MMT: manual muscle testing, FMA - UE: Fugl Meyer Assessment – Upper Extremity, sEMG : surface electromyography, K: kontraksi, LK: lama kontraksi, A: amplitudo

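### Six confounders are named, but four have no entry on the available form and no specified test uses any, so the study could not show that day-3 sEMG adds to stroke severity or lesion characteristics

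*Combined protocol and SAP*

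**What the plan says.** **The factors.** Under Study participants, the protocol names six confounding factors: stroke location, stroke size, spasticity, rehabilitation programme, "Compliance rehabilitation" and stroke risk factor. It does not say how any of them will be measured or controlled.

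**The form (Lampiran 1).** The basic-data block has "Faktor Risiko" (risk factors) and "Sisi Lesi Otak" (side of the brain lesion). The block headed "Pemeriksaan Fisik" holds vital signs, BMI, VAS and the NIHSS score. The visit table, "Penilaian dan Pemeriksaan MMT, FMA-UE dan sEMG", holds MMT, FMA-UE and three sEMG readings for each of five muscles. Table 4 (Operational Definition) defines stroke side, stroke severity by NIHSS, and risk factors. It does not define lesion size, spasticity, rehabilitation programme or compliance.

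**The analysis.** For two time points, the Data Analysis section says: "Numerical variables between pairs of two groups is compared using the paired T test if the data is normally distributed", with Wilcoxon as the alternative. For more time points: "Numerical variables between pairs of more than two groups is compared using the repeated ANOVA test", with Friedman as the alternative. Paired categorical data get McNemar or marginal homogeneity tests. No covariate, stratification, correlation or regression is mentioned. Table 3 lists risk factors and stroke side beside an empty p-value column, with no test, grouping or outcome named.

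**The concern.** The hypothesis is that sEMG predicts upper-limb recovery. The Problem Statement sets a higher bar: wearable sensors should tell clinicians something that current methods do not. That is a claim of added value. The literature review also says that patients with milder initial deficits tend to recover better. A patient with a small, mild stroke may therefore show both more early muscle activity and more recovery. An unadjusted association cannot tell whether sEMG carries its own information or stands in for severity or lesion size.

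The protocol recognises the issue by naming the factors, but provides neither the data nor the analysis to address it. At stake is whether the report can say anything about sEMG beyond what the NIHSS and the scan already show.

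**Working it through.** **1. Count of named factors against form, definitions and tests**

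| Factor | Available form | Table 4 | Used in a specified test |
|---|---|---|---|
| Stroke location | side only | side only | no |
| Stroke size | none | none | no |
| Spasticity | none | none | no |
| Rehabilitation programme | none | none | no |
| Rehabilitation compliance | none | none | no |
| Stroke risk factor | yes | yes | no |

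Four of six have no entry, one is partial and one is recorded. If location means lesion site rather than side, five are not captured. None is used in a specified test. The FMA-UE reflex item does not fill the spasticity gap: it is scored only after full marks in part IV and is not a spasticity scale.

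**2. The plan's own sample-size figure**

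((1.96 + 1.64) × 1 / 1)² = 12.96, so 13. Adding 10% gives 13 + 1.3 = 14.3, so 15. Both reproduce. The final 30 comes from a rule of thumb. The formula sizes a mean paired difference and makes no allowance for a prediction analysis or covariates.

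**3. How far a shared factor could move an unadjusted result (illustration)**

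The documents give no correlations, so these are assumptions. Suppose one factor correlates a with day-3 sEMG and b with 3-month FMA-UE, and sEMG adds nothing once that factor is known (partial correlation zero). The unadjusted correlation is then a × b. With n = 30, the Fisher z statistic centres on atanh(a × b) × √(30 − 3).

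- a = b = 0.4: r = 0.16; atanh(0.16) × √27 = 0.84; two-sided rejection at 5% is about 13.4%.
- a = b = 0.5: r = 0.25; atanh(0.25) × √27 = 1.33; rejection is about 26.4%.

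These are rejection rates when the null of no added prediction is true, against a nominal 5%.

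**4. What adjustment costs at n = 30**

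From the noncentral F test at two-sided 5% and 80% power, one sEMG predictor with no covariate can detect a correlation of about 0.468. With six one-degree-of-freedom covariates (22 residual degrees of freedom) the detectable partial correlation is about 0.472. At a fixed partial correlation, one added covariate costs almost nothing.

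Overlap between covariate and sEMG can widen the interval. If the covariate does not help explain the outcome, the standard error grows by 1/√(1 − a²): 1/√0.84 = 1.09 at a = 0.4, and 1/√0.75 = 1.15 at a = 0.5. If it does help explain the outcome, the growth is smaller.

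The harder limit is the number of sEMG measures. Five muscles × three parameters = 15; with six covariates, 8 residual degrees of freedom remain and the detectable partial R² is about 0.65. This favours one prespecified sEMG predictor and one covariate at a time.

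**The case against.** **Prediction is not causation.** The research question asks whether sEMG can predict recovery, not whether it does so independently of lesion size or therapy. A marker that tracks lesion size, and through it recovery, does predict recovery. This stands. A reader might infer that an unadjusted association would be spurious, or that 13% and 26% are false-positive rates for the study's hypothesis. The documents do not support that: under the stated null, a marginal correlation of 0.16 or 0.25 is a real association and those figures are power. The point is limited to added value, which the Problem Statement asks for.

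**Nothing planned is confounded in this way.** The specified tests compare patients with themselves over time. Fixed features such as lesion site and size do not differ between a patient's visits, and no planned test links early sEMG to later FMA-UE. The Study Variable section even lists sEMG as a dependent variable. This also stands. The missing prediction analysis is the larger gap and must be filled first; covariates alone would repair nothing.

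**The data are not lost.** A reader might infer that unrecorded factors cannot be recovered. For lesion site and size this is not so, because CT or MRI confirmation is an inclusion requirement. The risk applies to spasticity and rehabilitation received.

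**Not all six belong in a model.** Rehabilitation follows the day-3 recording, and the literature review describes spasticity as appearing weeks or months later. They are not baseline factors, so a demand to adjust for all six would go too far.

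**Absence is hard to prove.** Some appendix pages are not in the text available here, so a field there cannot be ruled out. Table 3's p-value column might also concern risk factors and side. It is undefined, however, and would not adjust a relation between sEMG and recovery.

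**Conclusion.** The point holds in a limited form. On the available text, four of the six named factors are not recorded, location is recorded by side only, and none enters a specified test. The study as planned could not show that day-3 sEMG adds to what severity or lesion characteristics already tell. It would not thereby be barred from a purely marginal claim of prediction, once an analysis for that claim exists.

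The count depends only on the documents, subject to the appendix pages not seen. The 13% and 26% rates depend on assumed correlations of 0.4 and 0.5 and on a null of no added prediction; they show scale and are not estimates for this study. The matter is minor beside the missing sEMG-to-recovery analysis. Label: cheap improvement.

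**What to change.** 1. First specify the analysis that relates day-3 sEMG to 3-month FMA-UE, with a prespecified sEMG predictor. None is planned now.
2. Add a sensitivity table that repeats that analysis with NIHSS, lesion site and lesion size entered one at a time. NIHSS is already on the form. Take site and size from the CT or MRI required at inclusion, and fix their coding in advance with few categories.
3. Add form lines for rehabilitation type and sessions attended, and for spasticity where routine care already assesses it. Report these descriptively, because they arise after day 3.
4. If these steps are not taken, state that no claim of prediction independent of these factors will be made.

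The cost is a few form lines, a reading of scans already available, minor data entry and one short table. Intervals in the adjusted analyses will usually be slightly wider. No extra patients or visits are needed.

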### **Sampling Technique**

The method of sampling based on consecutive samplings, that is, all stroke patients who meet the inclusion and exclusion criteria during the duration of the study.

## Study Variable

Independent variables:

1. Type of stroke
2. Stroke severity
3. Recurrent stroke

Dependent variables:

1. MMT score
2. FMA-UE score
3. Electrical activity of deltoid muscle
4. Electrical activity of biceps muscle
5. Electrical activity of triceps muscle
6. Electrical activity of wrist flexors muscle
7. Electrical activity of wrist extensors muscle

## Sample Size Determination

Samples are taken from research subjects that meet the inclusion criteria.

The sample size to test the pair averages then the large determination of the sample, carried out on the basis of statistical calculations by setting the 95% confidence level of the two-way hypothesis and the power test 95%.

Sample determination for categorical numerical analytical research pairs using the formula:

$$n_1 = n_2 = \left( \frac{(Z_\alpha + Z_\beta)S}{X_1 - X_2} \right)^2$$

Where:

$Z_\alpha$  = alpha standard deviation

$Z_\beta$  = beta standard deviation

$S$  = combined standard deviation.

$X_1 - X_2$  = average minimal difference that is considered significant

Type I error is determined as 5%, hence two-ways hypothesis  $Z\alpha = 1,96$

Type 2 error determined as 5%, hence  $Z\beta = 1,64$

Based on the formula, the value is entered into the sample size formula as follows:

$$n_1 = n_2 = \left( \frac{(Z_\alpha + Z_\beta)S}{X_1 - X_2} \right)^2$$

$$n_1 = n_2 = \left( \frac{(1,96 + 1,64) * 1}{1} \right)^2$$

$$= 12,96 \approx 13$$

The minimum sample size for the pre-post test group is 13 people. The minimum number of samples required is 13 samples. The minimum sample number is added to the 10% possibility of sample exclusion so that the minimum sample size is  $13 + 1.3 = 14.3 \approx 15$  samples.

According to Gay and Diehl (1992), the sample must be as large as possible. This opinion assumes that the more samples taken, the more representative they will be and the results can be generalized. The sample size depends on the type of research:

1. The research is descriptive, so the minimum sample = 10% of the population
2. Correlational research, minimum sample is 30 units
3. Comparative causal research, the sample is 30 units per group
4. Experimental research, the minimum sample is 15 units per group

Based on the opinion of Gay and Diehl (1992), the minimum sample for this study for comparative analysis is 30 people. Based on the formula above, the minimum sample size for this research is adequate, so the minimum sample size is 30 samples.

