### ***Study Objective***

The aim of the study are:

To know if sEMG parameters can predict upper extremity motor function recovery in acute stroke patients

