**Hypothesis :**

Based on the framework and premises above, the hypothesis is formulated as follows:

H0 : sEMG parameters cannot predicts upper extremity motor function recovery in stroke patients

H1: sEMG parameters can predicts upper extremity motor function recovery in stroke patients (premise 1,2,3,4,5)

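### The only aim is prediction, but no planned test relates sEMG to later recovery, and the stated 95% power concerns change over time

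*Combined protocol and SAP*

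**What the plan says.** **Aim.** Study Objective reads "To know if sEMG parameters can predict upper extremity motor function recovery in acute stroke patients". The Research Question asks the same thing, and the null hypothesis is that "sEMG parameters cannot predicts upper extremity motor function recovery in stroke patients". No second aim or hypothesis is stated.

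**Variables.** Study Variable puts type of stroke, severity and recurrence under independent variables. The sEMG signals, beginning with "Electrical activity of deltoid muscle", are under dependent variables together with MMT and FMA-UE.

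**Tests.** Data Analysis says "Numerical variables between pairs of two groups is compared using the paired T test if the data is normally distributed", with Wilcoxon as the alternative. It adds repeated ANOVA or Friedman for more than two time points, McNemar or marginal homogeneity for paired categories, and Shapiro-Wilk as a check of distribution. The note to Table 2 (Dummy Table) repeats the numerical tests.

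**Sample size.** The calculation is for paired averages, "setting the 95% confidence level of the two-way hypothesis and the power test 95" per cent. It uses a standard deviation of 1 and a difference of 1 and arrives at 13. Then "The minimum sample number is added to the 10% possibility of sample exclusion", which gives 15. A cited rule of thumb follows, from which "the minimum sample for this study for comparative analysis is 30 people". The same list gives 30 for correlational research. The section closes with "Based on the formula above, the minimum sample size for this research is adequate, so the minimum sample size is 30 samples".

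**The concern.** A mean change over time and a predictive association are different quantities. FMA-UE and sEMG amplitude could both rise in nearly every patient while the Day-3 signal says nothing about who recovers more. The named tests can establish the first and are silent on the second.

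Two consequences follow. The study can be completed exactly as planned without testing its only hypothesis. A reader may also take the 95% power, and the closing statement that the size is adequate, to cover prediction. If a prediction analysis is then added once data are in hand, it has no stated precision and no pre-named predictor among the 15 candidates (five muscles by three features).

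**Working it through.** **1. The plan's own figure.** Inputs from Sample Size Determination: Zα = 1.96, Zβ = 1.64, S = 1, difference = 1.

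- n = ((1.96 + 1.64) × 1 / 1)² = 12.96, rounded to 13.
- 13 + 1.3 = 14.3, rounded to 15.

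Both reproduce. The 30 does not follow from this formula.

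**2. What that figure covers.** With S read as the SD of the within-patient differences, exact paired-t power (noncentral t, two-sided 5%) for a change of 1 SD is 91.1% at n = 13, 94.9% at n = 15 and over 99.9% at n = 30. With 30 evaluable, 95% power is reached at a change of about 0.68 such SDs.

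The section calls S a combined standard deviation and does not say which SD is meant. If S is the SD of raw scores, the SD of differences is S × √(2(1 − ρ)), where ρ is the between-visit correlation. The documents do not give ρ; the values below are assumptions.

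| Assumed ρ | Change detectable at n = 30 with 95% power, in raw SDs |
|---|---|
| 0.3 | 0.68 × √1.4 ≈ 0.81 |
| 0.5 | 0.68 × √1.0 = 0.68 |
| 0.7 | 0.68 × √0.6 ≈ 0.53 |

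**3. Aim against tests.** The aim needs an analysis with early sEMG on one side and later recovery on the other. Each comparative test in Data Analysis takes one variable and compares it with itself at another visit. Table 2 has one row per variable and columns for visits, so it also has no cell for an association.

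**4. What 30 could support for prediction (illustration).** The documents give no target correlation, so r is assumed. The setting is one Day-3 sEMG parameter against 3-month FMA-UE, adjusted for Day-3 FMA-UE. On the Fisher z scale with one covariate, SE = 1/√(n − 4).

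- n = 30: SE = 1/√26 = 0.196. For 80% power, |r| = tanh((1.960 + 0.842) × 0.196) ≈ 0.50. For 95%, |r| = tanh((1.960 + 1.645) × 0.196) ≈ 0.61.
- n = 30, observed r = 0.5: tanh(0.549 ± 1.96 × 0.196) = 0.16 to 0.73.
- If only 27 had 3-month data: SE = 1/√23 = 0.209, thresholds about 0.53 and 0.64, and interval 0.14 to 0.74.

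| Assumed partial r | Power, n = 30 | Power, n = 27 |
|---|---|---|
| 0.3 | 35% | 32% |
| 0.4 | 58% | 53% |
| 0.5 | 80% | 75% |
| 0.6 | 94% | 91% |

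**5. Score or change.** If Y₃ = a + b·sEMG + c·Y₀ + e, then Y₃ − Y₀ = a + b·sEMG + (c − 1)·Y₀ + e. The sEMG coefficient b and its p value are therefore the same for the 3-month FMA-UE score and for FMA-UE change from Day 3.

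**The case against.** - **The plan's own source gives 30 for correlational research, so 30 meets it.** True. But the plan invokes the comparative line, and neither line carries an effect size, power or interval width.
- **Data Analysis says the analysis follows the objectives and hypotheses.** This shows intent, but it names no method. Table 3 has a p-value column but no sEMG variable. The conceptual-framework and flow figures are not shown, but the written list of tests is there.
- **The data can answer the question.** This stands. MMT, FMA-UE and sEMG are all scheduled at Day 3 and at 3 months. The gap is in the planned analysis, not in data collection.
- **A reader might infer that 30 is too small.** The documents do not support that. Earlier correlations are described only as modest (Problem Statement) or moderate (Surface Electromyography), without figures. For one strong association 30 could be enough.
- **A reader might infer that the plan leaves 27 evaluable, because 10% is added to 13 but not to 30.** That is not established either. The 10% is for exclusion, not for a missing 3-month visit; Sampling Technique sets no cap; and 30 is called a minimum. The figures for 27 are a scenario only.
- **The proposed model involves choices.** It does. Table 4 defines recovery in FMA-UE bands, although it also lists FMA-UE as numerical, and Study participants names six confounders that the model leaves out. Adjustment for Day-3 FMA-UE follows from the literature review, which says that milder initial deficits recover better. Another pre-specified model would also close the gap.

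**Conclusion.** The point holds and should be fixed. The main defect is the missing analysis: the plan states one hypothesis, about prediction, and names no test of it. The second is that the 95% power and the word adequate rest on a calculation for a different question, while the adopted 30 has no power or precision behind it. The arithmetic is correct for the question it addresses.

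The conclusion does not go as far as saying that the study is underpowered. What 30 can establish about prediction is simply not stated. The thresholds of about 0.50 and 0.61, and the interval of 0.16 to 0.73, rest on the assumed r, one covariate, one predictor, two-sided 5% and the Fisher approximation. The 0.68 SD figure rests on reading S as the SD of paired differences and covers a two-visit comparison only.

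**What to change.** **Data Analysis.** Add as the primary analysis a linear regression (or partial correlation) of 3-month FMA-UE on one Day-3 sEMG parameter, adjusted for Day-3 FMA-UE and reported with its 95% confidence interval.

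- Name the parameter before any follow-up outcome data are examined, including those at 1 and 2 months. Treat the other 14 muscle-by-feature parameters as exploratory.
- Show the Table 4 FMA-UE bands descriptively.
- Note that the model gives the same sEMG coefficient and p value for FMA-UE change from Day 3. This does not extend to the other rows of Table 2's change column, for which no reference visit is stated.
- State that a non-significant result is not evidence that sEMG does not predict recovery.

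**Study Variable.** List Day-3 sEMG as a predictor for this analysis.

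**Sample Size Determination.** Replace the closing sentence with text to this effect: *The 95% power applies to a paired change of 1 SD of the within-patient differences (about 0.68 such SDs with 30 evaluable) and does not address prediction. The 30 is a rule of thumb. As an illustration with r assumed, 30 evaluable patients and one covariate, 80% power needs a partial |r| of about 0.50 and 95% about 0.61; an observed partial r of 0.5 has a 95% confidence interval of about 0.16 to 0.73. If only 27 have 3-month data, these become about 0.53, 0.64, and 0.14 to 0.74.*

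**Cost.** Rewording, one added analysis on data already collected, the choice of one primary sEMG parameter, and a less favourable stated figure for the aim. No extra patients or visits.
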